with supportive nutrition skill-building activities, for low-income populations.[101] It is the only government-funded program of this type in Canada. Between 2007 and 2017, households received \$15/week. This amount was determined based on a U.S. farmers' market coupon program that provided on average \$10-30 for participants [102] and based on the availability of funds. The amount increased to \$21/week in 2017 to account for increased food costs. In 2018, the BC FMNCP served over 11,000 individuals, including 532 pregnant women, 1,084 seniors, and 4,965 children.[103] The program facilitates access to nutritious foods for low-income families, pregnant women, and older adults by providing participants with coupons valued at \$21/week to purchase fruits, vegetables, dairy, meat/poultry/fish, eggs, nuts, and cut herbs from participating BC farmers' markets.[101] Farmers' markets that participate in the BC FMNCP operate 1-2 days per week, with hours that vary by location. While coupons may only be redeemed from June to November, most communities offer indoor markets that are open year-round.[101, 104] The goal of the BC FMNCP is to provide financial support for low-income households to purchase and consume healthier foods, thereby improving diet quality [47, 105] and overall health.[106, 107] The program also aims to minimize further marginalization of low-income individuals by encouraging their participation in farmers' markets, which are important social spaces that may foster social and mental well-being.[54, 108, 109] Currently, the FMNCP operates in 57 BC communities and reaches over 3900 households;[101] however, the need remains substantial, with over 15 communities on waiting lists to participate. It is unclear if the BC FMNCP is achieving its aims, as the program's outcomes have not been rigorously investigated.

This study was co-designed with the BC Association of Farmers' Markets and the FMNCP in order to achieve the following objectives:

- 1) Conduct a RCT to examine the impact of the BC FMNCP on the following outcomes immediately post-intervention and at 16 weeks post-intervention among low-income adults:

- a. mean overall diet quality (primary outcome);
- b. mean diet quality subscores, mental well-being scores, sense of community, odds of experiencing household food insecurity and odds of malnutrition risk (secondary outcomes); and
- c. mean subjective social status (exploratory outcome)

METHODS

Study design

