The HEI-2015 encompasses thirteen dietary components to assess overall diet quality,[161] including nine 'adequacy' components (recommended foods/nutrients, including total fruits, whole fruits, total vegetables, greens and beans, whole grains, dairy, total protein foods, seafood and plant proteins, fatty acids) and four 'moderation' components (foods/nutrients recommended to limit, including refined grains, sodium, added sugars, saturated fats). Component scores are density-based and, therefore,

independent of energy intake.[161, 163] Diet quality (total HEI-2015 scores and subscores) will be calculated using the simple HEI scoring algorithm.[161] This method provides scores at the individual level and can, therefore, accommodate the multi-level nature of our data and include covariates.[161] HEI-2015 scores will be calculated using three nutrient databases linked to the ASA24-Canada-2018:[173] the Canadian Nutrient File and the U.S. Department of Agriculture's (USDA) Food and Nutrient Database for Dietary Surveys to convert dietary intakes to energy and nutrient intakes, and the USDA Food Patterns Equivalents Database to convert dietary intakes to dietary constituents (e.g., fruits) and measurement units consistent with HEI-2015 scoring standards (e.g., cup-equivalents of fruit).[162, 163, 174, 175] Ratios for each of the dietary constituents (e.g., quantity of fruit per 1000 kcal) will be calculated for each participant and scored using HEI-2015 scoring standards. The total score for each participant will be derived by adding the scores for intake of 'adequacy' and 'moderation' components with possible scores ranging from 0-100. A higher score indicates a higher quality diet.[161]

Statistical analyses

Descriptive analyses will be conducted to examine participant characteristics by group at each time point. Characteristics of study completers (i.e., provided data at Time 3) and non-completers will also be compared.

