Analyses will be intention-to-treat, in which participants will be analysed within the groups to which they were randomized regardless of adherence (e.g., failure to redeem coupons) or dropout. The analyses will include all participants who provided data at baseline. Repeated measures mixed-effect regression will assess differences in changes in mean HEI-2015 scores, HEI-2015 subscores, mental well-being, sense of community, and subjective social status between the FMNCP and control groups immediately post-intervention and 16 weeks post-intervention. Multinomial logistic regression will be used to assess

differences in the odds of experiencing household food insecurity and malnutrition risk for the FMNCP group compared to the control group immediately post-intervention and 16 weeks post-intervention. Statistical models will include intervention group (FMNCP vs control), time from baseline, intervention-by-time interaction, blocking variables (i.e., sex, rural/urban, pregnancy, breastfeeding), baseline values of the outcome, data collection mode (online, phone), household size, and place of data collection (community partner, other) as fixed effects covariates. Participant-specific (i.e., repeated measures) and rural/urban variations in outcomes will be modeled using random effects. Models will also include covariates specific to each outcome to increase the precision of estimates.[95] For the primary outcome of overall diet quality, models will include children living in the home (yes, no), sex, age, BMI, marital status, race/ethnicity, perceived health, smoking, day of dietary recall completion, and dietary recall number (i.e., dietary recall 1 or 2). Models that are and are not adjusted for an indicator of energy intake misreporting (the ratio of reported energy intake to total estimated energy expenditure) will be presented. Adjusted group differences (i.e., FMNCP vs control) in outcomes will be estimated using 95% confidence intervals and corresponding p-values.

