Subgroup analyses will examine whether the impact of the intervention on primary and secondary outcomes differs according to age group or sex. Dose-response analyses will examine whether the impact of the BC FMNCP on overall diet quality depends on the number of coupons redeemed and the number of nutrition skill-building activities attended. Interactions will be retained in statistical models if $p < 0.10$. Analyses will be conducted in Stata (v15.1, Stata Corp, TX, USA), with $p < 0.05$ indicating statistically significant differences between groups.

Missing data

Missing data will be handled using full information maximum likelihood under a missing at random assumption. We will also attempt to minimize missing data by reviewing all data within 24 hours of receipt and by contacting participants to fill-in missing or implausible responses within 48 hours. Participants who drop out of the study will be asked to provide reasons for drop out to assess the plausibility of a missing at random assumption.

Sensitivity analyses

Monte Carlo Markov Chain multiple imputation, inverse probability weighting and available case analysis will be used in a sensitivity analysis to investigate the impact of different assumptions about missing data on estimated program impacts.[176-178] Given the possibility of non-random attrition, pattern mixture methods models [179] will be used to explore the robustness of study findings to the assumption that data were missing not at random.[180]

Sample size calculation

The sample size was calculated from a RCT that investigated the impact of a fruit and vegetable rebate on HEI-2010 scores in low-income participants in the U.S.,[95] and a cross-sectional study that assessed average diet quality scores in disadvantaged Canadians.[36] In the RCT, diet quality in the intervention group was 4.7 points higher (95% CI 2.4, 7.1) at follow-up compared to controls.[95] This difference can be translated to, for example, an additional half serving of fruit per day, which is clinically meaningful and achievable.[107, 165] Assuming a type I error of 5%, an attrition rate of 30% by the 26- to 31-week follow up, and potential design effects based on sampling within different communities (estimated at 1.1, or an inflation of 10%), 264 participants are required for 80% power to detect a 4.7-point difference in diet quality.

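### Overall diet quality is primary at both Time 2 and Time 3 with no rule for which result carries the primary claim, and neither misreporting version of the model is labelled primary

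*Combined protocol and SAP*

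**What the plan says.** The objectives at the end of the Background cover "the following outcomes immediately post-intervention and at 16 weeks post-intervention among low-income adults". Mean overall diet quality is the primary outcome under that stem, so it is primary at both follow-up times. Study design places Time 2 at 10–15 weeks and Time 3 at 26–31 weeks.

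Statistical analyses uses a repeated measures mixed model to compare changes in HEI-2015 score "between the FMNCP and control groups immediately post-intervention and 16 weeks post-intervention". On its content: "Statistical models will include intervention group (FMNCP vs control), time from baseline, intervention-by-time interaction". On reporting: "Adjusted group differences (i.e., FMNCP vs control) in outcomes will be estimated using 95% confidence intervals and corresponding p-values". The section sets p < 0.05 for differences between groups. After the subgroup and dose-response sentences it adds: "Interactions will be retained in statistical models if" p < 0.10.

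For the primary outcome the same section announces: "Models that are and are not adjusted for an indicator of energy intake misreporting", the indicator being "the ratio of reported energy intake to total estimated energy expenditure". Both versions are to be presented, and neither is called the main one.

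Sample size calculation uses a 5% type I error, 80% power, a 4.7-point difference, 30% attrition by the 26- to 31-week visit and a design effect of 1.1, giving 264 participants. It names neither a time point nor a model version for the 4.7 points.

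**The concern.** The sample size is built for one test of one difference, but the analysis text yields two group contrasts on the primary outcome, each with its own p-value. Nothing says whether the trial meets its primary objective when Time 2 alone is significant, when Time 3 alone is, or only when both are. One set of results could therefore support different primary conclusions, and the error rate and power of the primary claim depend on a rule that is not written down.

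Two further gaps bear on the same claim. The p < 0.10 retention rule does not say whether it covers the intervention-by-time term. If it did, dropping that term would merge the two time-specific effects into one average, depending on the data. And if the models with and without the misreporting ratio disagree, the plan does not say which answers the primary question. At Times 2 and 3 the ratio's numerator, reported energy intake, comes from the same post-randomization recalls as the HEI score, so the programme could affect a variable that one version adjusts for.

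**Working it through.** **The plan's own figure.** The documents give no SD, so 264 cannot be reproduced independently; the SD can only be back-solved, taking the test as two-sided (sidedness is not stated).

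- Evaluable at Time 3: 264 × 0.70 / 1.1 = 168, or 84 per arm.
- SD = 4.7 × √(84/2) / (1.960 + 0.842) = 4.7 × 6.481 / 2.802 = 10.87.

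So 264 is consistent with one two-sided 0.05 test at 80% power if the SD is about 10.9 (an assumption). There is no allowance for a second primary test.

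**False-positive chance with no effect at either time.** The two test statistics are taken as bivariate normal with critical value 1.960. At correlation 0, P(either significant) = 1 − 0.95² = 0.0975. The documents give no correlation between the two contrasts, so a range is shown.

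| Assumed correlation | Either significant | Both significant |
|---|---|---|
| 0 | 9.75% | 0.25% |
| 0.3 | 9.5% | 0.5% |
| 0.5 | 9.1% | 0.9% |
| 0.7 | 8.3% | 1.7% |
| 0.9 | 7.0% | 3.0% |

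**Power if both times must be significant.** The full 4.7-point effect is assumed at each time. At Time 3 the noncentrality is 1.960 + 0.842 = 2.802, which is 80% power. At Time 2, with the same SD and attrition a, it is 2.802 × √((1 − a)/0.70). Values of a other than 30% are assumptions, because the plan gives attrition only for Time 3.

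| Time 2 attrition | Noncentrality | Time 2 power | Both significant, correlation 0.3 / 0.5 / 0.7 |
|---|---|---|---|
| 30% | 2.802 | 80% | 66.6% / 68.7% / 71.3% |
| 20% | 2.995 | 85% | 70.2% / 72.0% / 74.3% |
| 15% | 3.087 | 87% | 71.6% / 73.3% / 75.4% |
| 10% | 3.177 | 89% | 72.9% / 74.4% / 76.3% |

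The range is 67–71% with 30% attrition at both visits and 70–76% with 10–20% at Time 2.

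**Alpha split at 0.025 each.** The critical value is 2.241. Time 3 power is P(Z > 2.241 − 2.802) = 71%. Time 2 power with the noncentralities above is 77%, 80% and 83% for attrition of 20%, 15% and 10%.

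**Misreporting ratio.** No arithmetic is possible: the documents give neither the spread of the ratio nor any figure for how the programme might move it. The Healthy Eating Index-2015 section states: "Component scores are density-based", and on that ground treats the scores as independent of energy intake. That may limit the effect of adjusting for the ratio, but it does not show that the ratio itself is unaffected by the programme.

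**The case against.** The best defence is that the plan asks two separate questions, whether the programme works and whether its effect lasts, and commits to reporting both with confidence intervals. Two separately reported questions need not share one alpha, and no section says that a significant result at either time makes the trial positive. This stands in part. A reader might infer that the plan's type I error is 10%; the documents do not support that, because the 7–10% arises only under an either-time rule that they neither adopt nor exclude. The defence does not supply the missing rule, since both times sit under one primary outcome.

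A second defence is that the attrition allowance to 26–31 weeks makes Time 3 primary by implication. It fits equally well as a provision for the last visit, and the 4.7 points are tied to no time. The allowance does bear on power: applying 30% attrition at Time 2 as well is a worst case if fewer people have left by then. A flat statement that both-times power is 67–71% would therefore be too strong.

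A third is that the mixed model could test both times jointly. The text does not exclude this, but separate group differences with intervals and p-values make two contrasts the likelier reading.

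On misreporting, both versions are promised, so the plan does not permit either to be dropped. A reader might infer that the adjusted model is biased; the documents show only that the ratio could be affected and that neither version is labelled. Likewise, the position of the p < 0.10 rule suggests that it concerns subgroup and dose-response interactions. It cannot be said that the plan will drop the intervention-by-time term, only that it does not protect it.

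**Conclusion.** The omission is real and should be corrected. Two unadjusted contrasts serve one primary outcome, and nothing decides between them.

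Its size depends on the rule that is missing. Under an either-time rule the chance of a false-positive primary claim is about 7–10%, against the 5% used for sample size. Under a both-times rule false positives are rare (0.25–3.0% with no effect at either time), but power falls short of 80% by roughly 4 to 13 percentage points across the retention scenarios shown. These figures rest on assumed correlations, two-sided testing, the full 4.7-point effect at both times and, for the upper power range, assumed Time 2 attrition of 10–20%. The misreporting part is a labelling gap of unknown consequence.

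The document is dated October 2024, and the last planned data collection was February 2020. A reader might infer that results had been seen before the plan took this form. The documents do not say so, and the point does not rest on it.

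**What to change.** State in the SAP:

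1. Either name one time point as primary, tested by the model's group contrast at that time at two-sided 0.05, with the other secondary; or set a fixed order in which the second time is tested at 0.05 only if the first is significant. The sponsor chooses. Time 2 first suits the Background's question of whether effects last; the attrition allowance in the sample size points to Time 3.
2. The intervention-by-time term stays in the primary model whatever its p-value, and the p < 0.10 retention rule does not apply to it.
3. The model without the misreporting ratio is primary, and the adjusted model is a sensitivity analysis. This avoids conditioning the primary result on a variable measured after randomization.
4. Whether these choices were made without sight of results by group. If not, say that they were made afterwards and give both times and both models equal prominence.

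The cost is SAP wording only, with N at 264. With one named time point, the other is no longer a primary claim. With a fixed order, an effect present only at the second-tested time cannot be confirmatory; with the full effect at both times, the second is claimed as often as both are significant, 67–76% across the scenarios above. Splitting alpha at 0.025 each avoids the gate, but power falls to about 71% at Time 3, and is about 77–83% at Time 2 if attrition there is 10–20% (an assumption).

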Using a parallel group RCT, we will collect data at three time points: baseline (Time 1; 0 weeks, June 2019), immediately following the BC FMNCP (Time 2; 10-15 weeks, October 2019) and 16 weeks after the BC FMNCP ends (Time 3; 26-31 weeks, February 2020).

Program overview

The BC FMNCP functions through a collaborative partnership between the BC Association of Farmers' Markets, the BC Ministry of Health, farmers' markets and community partners (i.e., local non-profit organizations). The BC Association of Farmers' Markets supports, develops and promotes farmers' markets across BC [101] and oversees the operations of the FMNCP. The FMNCP is supported by the province of BC and the Provincial Health Services Authority. Community partners distribute coupons to program participants from their organization locations (e.g., pregnancy outreach and community services agencies) on a weekly or biweekly basis and offer nutrition skill-building activities such as cooking classes or community gardens to promote nutrition- and food-related knowledge and skills.[101]

Recruitment

The FMNCP Director will identify approximately 15 BC communities for the study (from the existing FMNCP and from program waiting lists) with the aim of achieving similar rural/urban coverage as the existing FMNCP. Within each community, the FMNCP director will recruit community partners by contacting those who are members of the BC Association of Farmers' Markets and offer nutrition skill-building activities for low-income groups. Community partners within study communities will be responsible for identifying and enrolling eligible low-income adults into the study from among their existing clients and will share study details via phone, email or in-person, using posters and other recruitment aids as needed. Community partners will assess eligibility using a screening questionnaire and will obtain voluntary, informed consent from eligible participants.

Eligibility criteria

Individuals will be eligible to participate if they meet the following criteria:

- Adults (≥ 18 years)
- Low-income as determined by community-specific thresholds (~\$18,000/year annual household income before taxes)
- No expected change in household income prior to study completion
- ≤ 8 people living in the home (including the participant)
- No expected change in household composition prior to study completion
- Primary food shopper for the household
- Does not self-report dementia or Alzheimer's Disease

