- Able to speak, read and write in English (or have someone who can assist them)
- No plans to move from principal residence prior to study completion
- Has not previously participated in the BC FMNCP

Randomization

Following baseline data collection, eligible participants will be randomized to the FMNCP group (n=132) or a no-intervention control group (n=132), with a 1:1 allocation ratio. An independent researcher from the Clinical Research Unit at the University of Calgary will generate a blocked randomization sequence that stratifies participants into blocks according to sex (male, female), geographic location (rural, urban), pregnancy (yes, no) and breastfeeding (yes, no). Blocked randomization will help to ensure balanced representation of participants in study arms.[110] REDCap (Research Electronic Data Capture), a secure, web-based data collection and management application [111] hosted at the University of Calgary, will be used to randomize participants into the FMNCP and control groups on the basis of this randomization sequence. The study coordinator will subsequently communicate participant group assignments to community partners and participants. Allocation concealment will be ensured via secure storage of the randomization sequence separately from the participant database, which will only be accessible by the study coordinator and the Clinical Research Unit. Researchers will remain blinded to respondent condition throughout the study. Although participants cannot be blinded to group allocation, they will be blinded to the specific study objectives to reduce expectancy bias, whereby communication of expected study outcomes influences participants' behaviour.[112-115]

Intervention

In the existing BC FMNCP, community partners distribute one to two sheets of coupons per week (each sheet contains \$21 in coupons) to program participants for a total of 16 sheets. Coupons can be used over 16-20 weeks to purchase fruits, vegetables, dairy, meat/poultry/fish, eggs, nuts, and cut herbs at participating BC farmers' markets. However, to allow sufficient time to recruit participants for this study, community partners will distribute 16 coupon sheets to the FMNCP group over 10-15 weeks (households with 5-8 individuals will receive 32 coupon sheets). To ensure participants receive all 16 coupon sheets,

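### Does the stable-household eligibility criterion shut out the pregnant participants that the randomization and the models provide for?

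*Combined protocol and SAP*

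**What the plan says.** Under Eligibility criteria, the combined protocol and SAP lists "No expected change in household composition prior to study completion". A separate item makes the same demand of household income, and another caps the number of people living in the home at eight. Household composition is not defined, and no exception for a birth is written. Under Recruitment, community partners check eligibility with a screening questionnaire.

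Study completion is most naturally Time 3. Study design places it 26-31 weeks after baseline, and Statistical analyses defines completers as those with data at Time 3.

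Other sections expect some participants to be pregnant. Randomization is stratified by sex, rural or urban location, pregnancy and breastfeeding. Statistical analyses enters as fixed effects the "blocking variables (i.e., sex, rural/urban, pregnancy, breastfeeding), baseline values of the outcome", along with household size and other terms. For diet quality, the "models will include children living in the home (yes, no), sex, age, BMI, marital status" and further characteristics.

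Two passages describe the existing programme. The Background says "The program facilitates access to nutritious foods for low-income families, pregnant women, and older adults" and "In 2018, the BC FMNCP served over 11,000 individuals, including 532 pregnant women, 1,084 seniors, and 4,965 children". Program overview gives "pregnancy outreach and community services agencies" as examples of the places from which coupons are handed out.

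**The concern.** Pregnancy is one of the few circumstances in which a new household member can be foreseen at screening. The neighbouring criterion counts people living in the home, so a newborn would naturally count. Taken at its word, the criterion removes most pregnant applicants, while the randomization and the models are set up as if they would be enrolled.

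If the literal reading applied, the pregnancy stratum would be very thin, adjusting for pregnancy would achieve little, and the results could not be extended to most pregnant clients of the programme. If partners in about 15 communities read the criterion differently, similar women would be admitted in one place and turned away in another. A birth during follow-up would also alter household size, children in the home and BMI, and would affect the malnutrition score, which is built from BMI and recent weight loss.

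**Working it through.** The plan gives no figure for the number of pregnant participants, so there is none to reproduce. The sample size of 264 is used below only as a multiplier; it does not depend on the pregnant share.

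**Inputs from the documents.** Time 3 at 26-31 weeks (Study design); 264 participants in two arms (Randomization); 532 pregnant women among over 11,000 people served in 2018, of whom 4,965 were children, and over 3,900 households currently reached (Background).

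**Assumptions not in the documents.** A 40-week term, and gestation at enrolment spread evenly from either week 0 or week 6 up to week 40.

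**Who is excluded on the literal reading.** A woman at gestation g is due before Time 3 if 40 − g is less than the follow-up time.

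- Follow-up of 26 weeks: excluded if g > 40 − 26 = 14.
- Follow-up of 31 weeks: excluded if g > 40 − 31 = 9.

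| Gestation spread from | 26 weeks | 31 weeks |
|---|---|---|
| Week 0 | 26/40 = 65% | 31/40 = 78% |
| Week 6 | 26/34 = 76% | 31/34 = 91% |

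If pregnancies came to notice only from week 12, the shares would be 26/28 = 93% and, because everyone is then past week 9, 100%. If completion meant Time 2 (10-15 weeks), they would run from 10/40 = 25% to 15/28 = 54%.

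**How many participants that could be.** Let p be the pregnant share of applicants and e the excluded share. Without the rule the expected number is 264p. With it, and with places refilled to 264, the number is 264 × p(1 − e)/(1 − pe). The last column uses e = 91% and e = 65%.

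| Denominator for p | p | Without the rule | With the rule |
|---|---|---|---|
| All people served | 532/11,000 = 4.8% | 12.8 | 1.2 to 4.6 |
| Non-children | 532/(11,000 − 4,965) = 8.8% | 23.3 | 2.3 to 8.6 |
| Households | 532/3,900 = 13.6% | 36.0 | 3.7 to 13.8 |

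The trial enrols one primary food shopper per household, so the household row belongs in the range. It assumes one pregnant woman per household and treats the 2018 count and the current household count as comparable. Both totals are stated as lower limits, so each p is approximate and tends to be high.

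**What this does to the stratification.** The pregnant strata number up to four (location by breastfeeding), or eight cells over two arms. Spread evenly, 13 to 36 women give 12.8/8 = 1.6 to 36.0/8 = 4.5 per cell. With the rule, the figure is 1.2/8 = 0.15 to 13.8/8 = 1.7. The cells are thin on either reading.

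**What depends on it.** The objectives concern low-income adults. The subgroup analyses cover age group and sex, and the dose-response analyses cover coupons and activities. None of these is an estimate for pregnant women. A sparse covariate category fixed before allocation does not bias the group comparison. Pregnancy and breastfeeding enter as blocking variables, and randomization follows baseline data collection, so they are naturally read as baseline values. Analysts would ordinarily take household size, children in the home and BMI at baseline as well.

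**The case for a change.** The best case for a change is that the criterion, the stratum and the covariate do not fit together on the page, and that one line would reconcile them. The literal reading removes more than half of pregnant applicants in every Time 3 case above, and the documents contain nothing that settles the intent. Pregnant women are a named group in the programme under evaluation, so readers have reason to ask whether the results apply to them.

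The ambiguity stands, but the conflict is weaker than it seems. Early pregnancies satisfy even the literal rule, so the stratum and the criterion can coexist. Stratifying by pregnancy is also evidence that the sponsor expected pregnant participants and did not intend an expected birth to disqualify them. Inconsistent screening is conjecture, because a questionnaire is used and it may state the rule. The references to pregnant clients and outreach agencies describe the existing programme; under Recruitment, trial partners are chosen for their association membership and their skill-building activities.

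Writing in an exemption for births would have a cost of its own. A stable household keeps fixed the size on which the number of coupon sheets depends and which the models use as a covariate. Exempting births gives up part of that stability, while holding to the rule gives up coverage of a small group. Either is defensible. Further additions, such as a malnutrition analysis without pregnant participants or a ruling on birth-related income change, concern few people and would be unlikely to alter a conclusion.

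**Conclusion.** This is an undefined term, and it does not call for a change to the plan. The literal rule would exclude about 65-91% of pregnant applicants, given a 40-week term, evenly spread gestation from week 0 or 6, and Time 3 as completion. The number of participants concerned is uncertain: 13 to 36 of 264 without the rule and 1 to 14 with it, if the trial resembled the programme. On either reading the treatment comparison is essentially unaffected, because the selection precedes randomization and no planned estimate rests on pregnant participants.

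The question left open is how far the findings extend to pregnant clients. Stating in the trial report whether an expected birth counted as a change in household composition, and limiting the conclusions if it did, answers it. Rewording the criterion now would probably gain nothing: the document is dated October 2024, and data collection was scheduled from June 2019 to February 2020. If those dates held, enrolment cannot be altered.
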